### Proprietary confidential information.

Doc. No.: U13-1326-02 Trial Protocol Page 94 of 95

[figure not shown]
Number of global amendment	3
8	In the event of force majeure or other disrupting circumstances (e.g. pandemic, war), physical patient visits to the sites may not be feasible or may need to be restricted to ensure patient safety. Based on a thorough assessment of the benefits and risks, the investigator may still decide to continue trial treatment. Where permitted by local law and regulations, trial medication may be shipped directly to the patients' home or two bottles of trial medication may be dispensed at the beginning of a treatment cycle, so that the next visit can be performed remotely.
Rationale for change	Experiences from the COVID-19 first wave situation; to allow flexibility in visit conduct in case required due to pandemic or other exceptional situations to ensure patients safety by ensuring continuous treatment.
Section to be changed	Section 6.1.2: Treatment and safety evaluation visits; Section 6.1.3: End of Treatment (EOT) visit
Description of change	The following statement has been added:  In the event of force majeure or other disrupting circumstances (e.g. pandemic, war,) patients visit may be performed remotely to collect/report study data such as adverse events, concomitant therapies, clinical evaluation of tumour by symptoms and study medication compliance check. Where permitted by local law and regulations, trial medication may be shipped directly to the patients' home or two bottles of trial medication may be dispensed at the beginning of a treatment cycle, so that the next visit can be performed remotely.
Rationale for change	Experiences from the COVID-19 first wave situation; to allow flexibility in visit conduct in case required due to pandemic or other exceptional situations to ensure patients safety by ensuring continuous treatment.
Section to be changed Description of change	9 References Updates of references

### Proprietary confidential information.

Boehringer Ingelheim 08 Feb 2021 BI Trial No.: 1200.55

Doc. No.: U13-1326-02 Trial Protocol Page 95 of 95

Number of global amendment	3
Rationale for change	Updates of references

2. LIST OF ABBREVIATIONS

Include a list of all abbreviations used in the TSAP

Term	Definition / description
AE	Adverse event
BAS	Biomarker analysis set
BRPM	Blinded report planning meeting
CR	Complete response
CTCAE	Common Terminology Criteria for Adverse Events
CTP	Clinical Trial Protocol
eCRF	Electronic case report form
ECG	Electrocardiography
ECOG	Eastern Cooperative Oncology Group
EGFR	Epidermal growth factor receptor
EMA	European Medicines Agency
EoT	End of treatment
HEP C	Hepatitis C
HIV	Human Immunodeficiency Virus
ICH	International Conference on Harmonisation
IPV	Important protocol violation
Max	Maximum
MedDRA	Medical Dictionary for Regulatory Activities
mg	Milligram
MI	Myocardial infarction
Min	Minimum
mRNA	Messenger Ribonucleic Acid
N	Denotes number of patients
NSCLC	Non-small cell lung cancer
IPV	Important protocol violation
OR	Objective response
OS	Overall survival
PD	Progressive disease

Term	Definition / description
PFS	Progression-free survival
PR	Partial response
PP	Per-protocol
PT	Preferred term
SAE	Serious adverse event
SD	Standard deviation
SD	Stable disease
SOC	System organ class
TKI	Tyrosine kinase inhibitor
TS	Treated set
TSAP	Trial statistical analysis plan
TTSP	Time to symptomatic progression

3. INTRODUCTION

[figure not shown]
As per ICH E9, the purpose of this document is to provide a more technical and detailed elaboration of the principal features of the analysis described in the protocol, and to include detailed procedures for executing the statistical analysis of the primary and secondary variables and other data.

This Trial Statistical Analysis Plan (TSAP) assumes familiarity with the Clinical Trial Protocol (CTP), including Protocol Amendments. In particular, the TSAP is based on the planned analysis specification as written in CTP Section 7 “Statistical Methods and Determination of Sample Size”. Therefore, TSAP readers may consult the CTP for more background information on the study, e.g., on study objectives, study design and population, treatments, definition of measurements and variables, planning of sample size, randomization.

SAS® Version 9.2 or higher will be used for all analyses.

4. CHANGES IN THE PLANNED ANALYSIS OF THE STUDY

Section 7.3.2 of the CTP describes the “Secondary Analysis” of the efficacy endpoints. It was decided to consider the efficacy endpoints as further endpoints rather than secondary endpoints due to disclosure requirements. Hence this TSAP describes these efficacy endpoints as further endpoints in [Section 5.3 \(Further Endpoints\)](#).

5. ENDPOINTS

This is an open-label, multi-centre, non-randomised, uncontrolled, single arm trial designed to evaluate the safety, tolerability and anti-tumour activity of afatinib (Giotrif®) in patients with locally advanced or metastatic non-small cell lung cancer (NSCLC) harboring EGFR mutation(s) and have never been treated with an EGFR-TKI. After the initial screening visit, patients will enter the open-label treatment period with safety visits at approximately every 28 days until the end of the trial. The trial objective is to evaluate the safety tolerability and anti-tumour activity of afatinib (Giotrif®) in this cohort of patients. Of main interest are AEs, collected throughout the study.

No specific tumour measurements are required in this program. Disease assessment will be based on the assessment of cancer related symptoms, tumour assessment (clinical, radiological or other), overall clinical benefit and, if available, radiologic assessments as per standard of care at the site. Data on tumour response, progression-free survival (PFS) and overall survival (OS) will be collected where possible.

5.1 PRIMARY ENDPOINT

The number of patients with adverse events according to CTCAE V 3.0.

[figure not shown]
5.2 SECONDARY ENDPOINTS

5.2.1 Key secondary endpoints

[figure not shown]
There are no key secondary endpoints.

5.2.2 Secondary endpoints

There are no secondary endpoints.

Proprietary confidential information © 2017 Boehringer Ingelheim International GmbH or one or more of its affiliated companies

6. GENERAL ANALYSIS DEFINITIONS

6.1 TREATMENT

There is only one treatment in this study, which is afatinib. The starting dose for all patients is 40 mg with an option to reduce the dose to 30 mg or reduce further to 20 mg from 30 mg based on individual tolerability. Unless otherwise stated, for all analyses, treated patients will be presented under the starting dose.

The following study periods based on key visit dates and actual start and stop dates of study treatment administration are defined:

- Screening: From day of informed consent to day prior to starting study treatment.
Special handling rule:
If informed consent date = date of first administration of study treatment, derive start of screening phase on the day of informed consent – 1 day.
- On-treatment: From day of first administration of study treatment to the day of last administration of study treatment.
- Residual effect period: From day after last administration of study treatment to the 28th day after last administration of study treatment
- Follow-up: After the residual effect period and up to the last per protocol contact if last per protocol contact is after residual effect period.
- Post-study: After the last per protocol contact or residual effect period (if last per protocol contact is same as 28th day after last administration of study treatment) but entered in the database before database lock.

For safety summaries, data recorded up to 28 days after last administration of study treatment will be considered as on-treatment (i.e. the actual on-treatment and residual effect periods defined above will be combined into one ‘on-treatment’ analysis period).

Safety data recorded after the residual effect period and up to the last per protocol contact will be listed as follow-up events. Those recorded after the last per protocol contact but entered in the database before lock will be listed as post-study events but not tabulated.

6.2 IMPORTANT PROTOCOL VIOLATIONS

No per protocol (PP) analysis will be performed for this study; however patients with potentially important protocol violations (IPVs) will be documented. The following list of potentially IPVs will be used; note that this is a working list and may not be finalised until the final Blinded Report Planning Meeting (BRPM) prior to database lock.

Table 6.2: 1 Important protocol violations

Category / Code	Description	Comment/Example	Efficacy/ Safety
A	Entrance Criteria Not Met		
A1	Inclusion Criteria Not Met		
A1.1	Locally advanced or metastatic Non-Small Cell Lung Cancer (NSCLC)	Inclusion criterion IN1 not met	E
A1.2	Epidermal Growth Factor Receptor (EGFR) mutation-positive result per the institution's testing methodology.	Inclusion criterion IN2 not met or EGFR mutation positive result is marked as No	E
A1.3	Male or female patients age ≥ 18 years	Inclusion criterion IN3 not met or patient's age < 18 years	E/S
A1.4.1	Adequate organ function as defined in protocol version 1	Inclusion criterion IN4 not met	E/S
A1.4.2	Adequate organ function as defined in protocol version 2	Inclusion criterion IN4 not met	E/S
A1.5	ECOG score between 0 – 2	Inclusion criterion IN5 not met or Baseline ECOG score not between 0-2	E
A2	Exclusion Criteria Met		
A2.1	prior treatment with an EGFR tyrosine kinase inhibitor (TKI)	Exclusion criterion EX1 met	E
A2.2	Anti-cancer treatment within 2 weeks prior to start of trial treatment	Exclusion criterion EX2 met	E
A2.3	Radiotherapy within 14 days prior to drug administration	Exclusion criterion EX3 met	E
A2.4	Major surgery within 4 weeks before starting trial treatment or scheduled for surgery during the projected course of the trial	Exclusion criterion EX4 met	E/S
A2.5	Known hypersensitivity to afatinib or any of its excipients	Exclusion criterion EX5 met	S
A2.6	History or presence of clinically relevant cardiovascular abnormalities or MI within 6 months prior to starting trial treatment	Exclusion criterion EX6 met	S
A2.7.1	Women of child-bearing potential and men who are able to father a child, unwilling to use adequate contraception prior to trial entry, for the duration of trial participation and for at least 2 weeks after treatment has ended (protocol version 1).	Exclusion criterion EX7 met	S
A2.7.2	Women of child-bearing potential and men who are able to father a child, unwilling to use adequate contraception prior to trial entry, for the duration of trial participation and for at least 28 days after treatment has ended (protocol version 2).	Exclusion criterion EX7 met	S

Table 6.2: 1 Important protocol violations (cont.)

Category / Code	Description	Comment/Example	Efficacy/ Safety
A2.8	Women of child-bearing potential who are nursing or pregnant or do not agree to submit to pregnancy testing as required by this protocol	Exclusion criterion EX8 met	S
A2.9	Any history of or concomitant condition that, in the opinion of the investigator, would compromise the patient's ability to comply with the trial or interfere with the evaluation of safety for the trial drug	Exclusion criterion EX9 met	E/S
A2.10	Previous or concomitant malignancies at other sites, except effectively treated non melanoma skin cancers, carcinoma in situ of the cervix, ductal carcinoma in situ or effectively treated malignancy that has been in remission for more than 3 years and is considered to be cured.	Exclusion criterion EX10 met	E/S
A2.11	Requiring treatment with any of the prohibited concomitant medications that cannot be stopped for the duration of trial participation	Exclusion criterion EX11 met	E
A2.12	Known pre-existing interstitial lung disease	Exclusion criterion EX12 met	S
A2.13	Presence of poorly controlled gastrointestinal disorders that could affect the absorption of the trial drug	Exclusion criterion EX13 met	E
A2.14	Active hepatitis B infection, active Hepatitis C (HEP C) and/or known Human Immunodeficiency Virus (HIV) carrier.	Exclusion criterion EX14 met	S
A2.15	Meningeal carcinomatosis	Exclusion criterion EX15 met	E/S
A2.16	Symptomatic brain metastases	Exclusion criterion EX16 met	E/S
B	Informed Consent		
B1	Informed consent not given	Inclusion criterion IN6 not met or Written informed consent by patient or guardian prior to admission into the trial is not given.	S
B2	Informed consent given too late	Inclusion criterion IN6 not met	S
B3	Incorrect or not updated Informed consent given		S
B4	Informed consent conducted by staff not on trial staff list		S
B5	Incomplete informed consent		S
B6	Informed consent not completed by patient		S

Table 6.2: 1 Important protocol violations (cont.)

Category / Code	Description	Comment/Example	Efficacy/ Safety
C	On Study		
C1	Serious GCP non-compliance [e.g. delayed SAE reporting, expired drugs, incorrect trial medication dose, source data not available]		S
C2	Incorrect timing of measurements at visit days		S
C3	Other PV affecting efficacy and possibly safety		E/S
C4	Other PV affecting safety only		S

Note: Missing visits, evaluations, and tests will be considered missing data, not protocol violations. All the potential IPVs listed in the table will be identified programmatically.

6.3 PATIENT SETS ANALYSED

Enrolled set (ES)

The enrolled set consists of all patients who signed informed consent.

Treated set (TS)

All planned analyses will be based on the Treated Set (TS) which includes all patients who were dispensed study treatment (afatinib) and are documented to have taken at least one dose of study treatment (afatinib).

6.5 POOLING OF CENTRES

This section is not applicable because there will be no pooling of centres or countries and no modelling thereof.

6.6 HANDLING OF MISSING DATA AND OUTLIERS

Missing or incomplete AE dates are imputed according to BI standards (see “Handling of missing and incomplete AE dates”).[\(1\)](#)

For efficacy data, the following rules will apply:

- For PFS, duration of objective response and duration of disease control, if a patient is **known** to have progressed during the treatment period, but the date of progression is not attainable, the following sequence for imputation of progression date will be followed:
 - Use the date of cancer-related symptoms assessment or visit date in which the progression was recorded (whichever is earliest).
 - If this is missing, the last known visit date or cancer related symptoms assessment date prior to the recorded progression (regardless of the disease assessment result at that visit) will be used.
 - If any such patient has no visit date or cancer related symptoms assessment date recorded at all, the date of first administration of study medication will be used as the date of disease progression.
- For overall survival, if a patient is known to have died (due to any cause), but date of death is not attainable, the last date when the patient is known to be alive will be used as date of death.

For partial treatment discontinuation date, the following logic is applied:

If month and year are known but day is missing, then use date of death if within the same month for a patient who died. Otherwise use last day of the month.

Missing biomarker values will not be imputed.

6.7 BASELINE, TIME WINDOWS AND CALCULATED VISITS

Baseline is defined as the last non-missing value prior to first administration of afatinib.

The time windows for subsequent clinic visits is 28 -7/+2 days. The end of treatment (EoT) visit can be anything up to a maximum of 14 days after the last intake of afatinib and the follow-up visit should be between 21 and 28 days after the EoT visit.

Nominal visit numbers as recorded in the eCRF will be used where required and there will be no windowing.

Study day will be calculated relative to the date of the first administration of afatinib. The day prior to first administration of afatinib will be 'Day -1' and the day of first administration of afatinib will be 'Day 1'; therefore 'Day 0' will not exist.

7. PLANNED ANALYSIS

Unless otherwise stated, for end of text tables, the set of summary statistics is: N / Mean / SD / Min / Median / Max.

For tables that are provided for endpoints with some extreme data, median, quartiles and percentiles should be preferred to mean, standard deviation, minimum and maximum.

Tabulations of frequencies for categorical data will include all possible categories and will display the number of observations in a category as well as the percentage (%) relative to the respective treatment group, unless otherwise stated. Percentages will be rounded to one decimal place. The category missing will be displayed only if there are actually missing values.

7.1 DEMOGRAPHIC AND OTHER BASELINE CHARACTERISTICS

Only descriptive statistics are planned for this section of the report. Demographic and baseline characteristic parameters collected and to be presented include:

- Age [years]
- Age class ($<65, \geq 65$ years and $<75, \geq 75$ years)
- Gender (*Male, Female*)
- Race (as defined in the eCRF)
- Country
- Height [cm]
- Weight [kg]
- Body mass index [kg/m²] (defined as weight [kg]/(height [cm]/100)²)
- Body surface area [m²] (defined as: 0.007184*(height^{0.725})*(weight^{0.425}))
- Smoking status (*Never-smoked, Ex-smoker, Current smoker*)
- Smoking history [pack-years]
- Baseline ECOG score
- EGFR mutation type: common, uncommon only
- Oncology history details
 - Previous therapies:
 - Systemic chemotherapies
 - Other anti-cancer therapies
 - Radiotherapies (listed only)
 - Previous surgeries for trial disease

This section will include a summary of all the subgroup variables detailed in [Section 6.4\(Subgroups\)](#). This is presented based on treated set.

It is expected that biomarker values will only be available for a subset of the study population. Therefore, demographics and baseline characteristics will be provided for the BAS as well and compared with the study population.

7.2 CONCOMITANT DISEASES AND MEDICATION

Only descriptive statistics are planned for this section of the report. Only concomitant therapies for rash and diarrhoea were collected on the eCRF and will be summarised.

For baseline conditions and signs and symptoms of the trial disease also only descriptive statistics will be presented.

7.3 TREATMENT COMPLIANCE

There is no analysis planned for treatment compliance as no data on compliance is collected.

7.4 PRIMARY ENDPOINT

Refer to [Section 7.8 \(Safety Analysis\)](#).

[figure not shown]
7.5 SECONDARY ENDPOINTS

[figure not shown]
7.5.1 Key secondary endpoints

[figure not shown]
This section is not applicable as no key secondary endpoints have been specified in the protocol.

[figure not shown]
7.5.2 Secondary endpoints

[figure not shown]
This section is not applicable as no secondary endpoints have been specified in the protocol.

7.7 EXTENT OF EXPOSURE

Total treatment time (days) will be calculated for each patient; total treatment time will include any dose interruptions or off-drug periods.

The definition of exposure is:

Treatment stop date – treatment start date + 1

In case of death (due to any cause), the treatment stop date will be imputed as the earlier of (date of last administration of afatinib, date of death) + 1 day.

Standard descriptive summaries of these data will be provided for the treated set of patients.

Total treatment time (days) will be summarized by afatinib dose level (40 mg, 30 mg, 20 mg and total), and by number of therapy lines at the 40 mg dose. The number of therapy lines for afatinib will be derived as: the number of all previous therapy lines + 1. The number of all previous therapy lines that the patient received prior to the start of treatment includes number of lines of all of the following:

- Systemic chemotherapies: count the number of previous chemotherapies with “therapy mode” as “advanced/palliative” on the previous chemotherapies eCRF page. If “therapy mode” is “neo-adjuvant” or “adjuvant” and taken within 1 year prior to study enrolment, then count them as a separate “line of therapy”.
- Other anti-cancer therapies: count the number of anti-cancer therapies with “therapy mode” as “advanced/palliative” on the other anti-cancer therapies eCRF page. If “therapy mode” is “neo-adjuvant” or “adjuvant” and taken within 1 year prior to study enrolment, then count them as a separate “line of therapy”. If there is a therapy with the same name and same start and end dates as a therapy present in previous systemic chemotherapies eCRF page, then ignore this as it has already been counted earlier.

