6.2.4 Follow-Up

The Follow-up (FU) visit should occur 28 (-7) days after the EOT visit.

Follow-up visits should be scheduled for patients who met the trial withdrawal criteria (see Section 3.3.4). This visit marks the end of the patient's participation in the trial. Patients will not be required to attend the clinic for this visit. The clinic staff will contact the patients or their caregivers by telephone and inquire about any adverse events that might have occurred since the last visit and if applicable follow up on any unforeseen pregnancy during the trial. All concomitant medication should be added to the patient's chart. The Patient Status eCRF will be completed at this time.

Any additional (unscheduled) follow-up visits should be scheduled for patients with unresolved SAEs, AEs, or laboratory abnormalities who have discontinued trial participation. These events must be followed until resolution or until agreement is reached between the local medical monitor and the investigator that further follow-up is no longer required.

Doc. No.: U13-1326-02 Trial Protocol Page 57 of 95

Table 6.2.4: 1 Follow-up (FU) Visit/EOT + 28 Days (-7)

	What to Include in the Patient's Chart	What to include in eCRF
Adverse events	Patients should be asked to report any hospitalizations, emergency treatments, or new medications as well as any general health issues that may have surfaced since their last visit. All the information collected should be recorded in the patient's chart. Refer to Sections: 5.2.2 and 5.2.2.2 for protocol specific requirements regarding the collection and reporting of adverse event information.	All relevant AEs and all SAEs.
Concomitant Medications	Patients should be asked to report any concomitant drug use (including, but not limited to,: non-prescription medications, anaesthetic agents, homeopathic/herbal remedies and dietary supplement preparations).	No concomitant medications will be recorded on eCRFs.
Patient Status	Document any information regarding the patient's status during the planned observation time (i.e., 28 days after the patient's last dose of medication).	Any new anti-cancer medication that the patient has taken since EOT visit.
	When applicable, every effort should be taken to collect and document information on date of death.	Date when the patient completed the planned observation time.
	Note: any AE which results in death is considered an SAE.	Date of death Patient's status

Page 58 of 95

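### SAP 7.7 as worded adds a redundant exposure day for recorded deaths, and SAP 6.6 completes partial stop dates without using the end-of-treatment visit as an upper bound (low severity)

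*SAP*

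**What the plan says.** **Exposure.** SAP 7.7 defines treatment time as "Treatment stop date – treatment start date + 1". The next sentence opens with "In case of death (due to any cause" and a closing bracket, and continues that "the treatment stop date will be imputed as the earlier of (date of last administration of afatinib, date of death) + 1 day". The results go into descriptive summaries for the treated set.

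**Study periods.** SAP 6.1 builds these on "actual start and stop dates of study treatment administration". Its on-treatment period runs "From day of first administration of study treatment to the day of last administration of study treatment", with no added day.

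**Date of death.** Protocol Table 6.2.4: 1 asks at the follow-up contact that "every effort should be taken to collect and document information on date of death". Deaths after the end of treatment can therefore be on file.

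**Partial stop dates.** Where month and year of discontinuation are known but the day is missing, SAP 6.6 says "then use date of death if within the same month for a patient who died. Otherwise use last day of the month". It names no other limit.

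**EoT visit.** SAP 6.7 says "The end of treatment (EoT) visit can be anything up to a maximum of 14 days after the last intake of afatinib"; Protocol 6.1.3 gives the same 0 to 14 days. Protocol Table 6.2.3: 1 records one stop date at termination, the day the last dose was swallowed, so this is most likely the date that SAP 6.6 completes.

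**The concern.** There are two separate issues, and they differ in kind.

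1. The death rule in SAP 7.7 is wrong as written. The formula is inclusive, so a stop date equal to the last-dose day already counts that day. Moving the stop date one day later for patients who died counts a day on which no dose was taken. Two patients with the same first and last dose then get different exposure only because one of them died, possibly weeks after stopping.

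2. The partial-date rule in SAP 6.6 is a defined, reproducible choice, but it leaves out information already in the database. The last dose cannot come after the EoT visit, yet the month-end date can.

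At stake are the treatment-time tables and, for the second issue only, possibly the end of the 28-day treatment-emergent window. Both rules can only lengthen treatment time. No hypothesis is tested, and SAP 7.8.1 counts patients with events, so treatment time is not a denominator in the visible text.

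**Working it through.** The plan states no exposure figure to reproduce, so the rules are applied to test dates.

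**Point 1, SAP 7.7**

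Inputs: exposure = stop − start + 1; stop after a death = min(last dose, death) + 1 day. Take start 1 March and last dose 10 March, which is 10 inclusive days.

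- Alive: stop 10 March; 10 − 1 + 1 = 10 days.
- Died 2 April, in follow-up: stop = min(10 March, 2 April) + 1 = 11 March; 11 days.
- Died 10 March: stop = 11 March, the day after death; 11 days.

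With consistent data a last dose never follows death, so the minimum is always the last-dose day. The literal rule is then last dose plus one for every recorded death.

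- One patient: +1 day, or 1/28 = 3.6% of a treatment time of one 28-day cycle, and less for longer treatment.
- Mean exposure: shift = f × 1 day, where f is the share of patients with a recorded death. The documents do not give f. For assumed f of 10%, 50% and 100%, the shift is 0.1, 0.5 and 1.0 day. Over the 481 patients in the protocol synopsis that is about 48, 240 and 481 patient-days.

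If the rule applies only where the last-dose date is missing, the minimum reduces to the date of death. The stop date is then always the day after death, so the extra day is still not needed.

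**Point 2, SAP 6.6**

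Overstatement = month end − true last dose. Over a 365-day year this sums to 7 × 465 + 4 × 435 + 378 = 5,373 days, for the seven 31-day months, the four 30-day months and February. The mean is 5,373/365 = 14.7 days and the maximum 30.

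For illustration only, assume the last-dose day is uniform over the year and the EoT lag is uniform over 0 to 14 days (365 × 15 = 5,475 cases):

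- The month-end date falls after the EoT visit in 73.7% of cases (96.7% with the lag fixed at 0 days, 50.7% with it fixed at 14).
- With the date capped at the EoT visit, the mean overstatement is 5.8 days and the maximum 14.
- If only a share s of these patients had an EoT visit, the mean after capping is 14.72 − s × 8.95. For s = 100%, 75%, 50% and 0% this gives 5.8, 8.0, 10.2 and 14.7 days.

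If the imputed date also served as last intake, the 28-day window could run to day 28 + 30 = 58 after the true last dose. The latest scheduled follow-up contact is at about day 14 + 28 = 42, so events from day 29 to about day 42 could be counted as treatment-emergent. The cap reduces this but does not remove it: an on-schedule visit at day 14 still allows 28 + 14 = 42.

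**Both rules together**

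This applies only if the imputed date enters SAP 7.7. Start 1 March, true last dose 10 March with the day missing, death 20 March: SAP 6.6 gives 20 March and SAP 7.7 then gives 21 March, so 21 days against a true 10.

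**The case against.** **The sentence may be harmless in intent.** It speaks of imputing a date, and SAP 6.6 uses that language for missing or incomplete values, so it may cover only deaths without a recorded stop date. Or the added day may simply restate the plus one of the formula. Either is possible, but the SAP says neither, and the brackets put the added day outside the minimum. Under the first reading fewer patients are affected and the day is still redundant. Under the second, deleting it changes nothing. What stands is that one day for every recorded death holds on the literal reading and is not an established effect.

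**High death shares are unlikely to be observed.** Under Protocol 6.2.4 participation ends at the follow-up contact, up to 28 days after the EoT visit, and under Protocol 3.3.4.1 patients may leave alive for another supply of afatinib. This stands: the 50% and 100% scenarios mark the edge of the range and are not forecasts.

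**The partial-date rule is not an error.** Agreed. The last-dose date is an eCRF item, so affected patients may be very few. A 14-day ceiling after capping also holds only if the EoT visit is on schedule; otherwise the ceiling is the actual gap. The uniform lag is arbitrary too. Protocol 6.2.3 wants the visit as soon as treatment stops, and shorter gaps would make the cap more useful.

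**Unseen text may settle it.** SAP 7.8.1 refers to a technical TSAP, and parts of the SAP are redacted. Either could resolve either point.

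**Conclusion.** Point 1 holds as a wording error: the death rule and the inclusive formula together count a day that SAP 6.1 does not. On the literal reading the size is one day per patient with a recorded death and at most 1 day on mean exposure. It affects descriptive exposure tables only, because SAP 7.8.1 runs the adverse-event window from last intake and not from this stop date.

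Point 2 holds as a cheap improvement. The overstatement can reach 30 days for an affected patient now; with the bound it is limited to the actual gap between last dose and EoT visit. The number of affected patients is not in the documents.

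Two stronger conclusions are tempting and not supported. One is that the primary safety results are biased. SAP 6.1 relies on actual stop dates and does not say what applies when that date is partial, so an effect on the 28-day window is conditional on the imputed date serving as last intake. The other is that exposure is materially inflated across the trial; the figures above show a small effect for point 1 and an unknown, possibly negligible, one for point 2. Overall severity is low.

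**What to change.** **SAP 7.7.** Delete the added day, so that the stop date after a death is the earlier of last dose and death. State whether the rule applies to all deaths or only where the last-dose date is missing.

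**SAP 6.6.** Where an EoT visit date exists, complete a partial discontinuation date with the earliest of month end, EoT visit date and date of death, but never before the first day of the recorded month or the treatment start date. The lower limit binds in none of the 5,475 illustrative cases; it only guards against conflicting entries. Where there was no EoT visit, keep the current rule. Add one sentence saying whether the completed date also serves as last intake for the 28-day window.

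The cost is a few lines of SAP text and programming, with no new data, since the EoT visit date and date of death are already collected. If the technical TSAP already contains the bound, a cross-reference is enough for that part.
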